4.1.8 Laboratory Requirements
 (must be done within 7 days prior to enrollment)

Hematology	Absolute neutrophils	$\geq 1.5 \times 10^9/L$
	Platelets	$\geq 100 \times 10^9/L$
Chemistry	Bilirubin	$\leq 1.5 \times \text{ULN}$ (upper limit of normal)*
	AST and ALT	$\leq 2.5 \times \text{ULN}$ $\leq 4.0 \times \text{ULN}$ if patient has liver metastases
	Serum creatinine or: Creatinine clearance**	$\leq 1.5 \times \text{ULN}$ $\geq 50 \text{ mL/min}$
* If confirmed Gilbert's, eligible provided $\leq 3 \times \text{ULN}$. ** Creatinine clearance to be measured directly by 24 hour urine sampling or as calculated by Cockcroft and Gault equation below: Females: $\text{GFR} = 1.04 \times (140 - \text{age}) \times \text{weight in kg} / \text{serum creatinine in } \mu\text{mol/L}$		

4.1.9 Patients must be able to swallow oral medications and have no known gastrointestinal disorders that may interfere with absorption (such as malabsorption).

4.1.10 Previous Therapy

Chemotherapy:

Patients must have had at least 1 prior line of cytotoxic chemotherapy for breast cancer, in any setting, which must have included an anthracycline and a taxane (unless contraindicated). Select patients that have not received both anthracycline and taxane therapy may be considered eligible after discussion with CCTG. There is no limit to the number of prior chemotherapy regimens.

Other Systemic Therapy:

Patients may have received other therapies including endocrine therapy and/or targeted therapies (including CDK4/6 inhibitors and PARP inhibitors).

Patients may not have received prior immunotherapies of any kind, nor any agent targeting PLK4.

Patients must have recovered (to at least grade 0 or 1) from all reversible toxicity related to prior chemotherapy or systemic therapy and have adequate washout as follows:

Longest of one of the following:

- Two weeks,
- 5 half-lives for investigational agents,
- Standard cycle length of standard therapies.

Radiation:

Prior external beam radiation is permitted provided a minimum of 28 days (4 weeks) have elapsed between the last dose of radiation and date of enrollment. Exceptions may be made for low-dose, non-myelosuppressive radiotherapy after consultation with CCTG. Concurrent radiotherapy is not permitted.

Surgery:

Previous surgery is permitted provided that a minimum of 21 days (3 weeks) have elapsed between any major surgery and date of enrollment, and that wound healing has occurred.

- 4.1.11 Patient consent must be appropriately obtained in accordance with applicable local and regulatory requirements. Each patient must sign a consent form prior to enrollment in the trial to document their willingness to participate.
- 4.1.12 Patients must be accessible for treatment and follow-up. Patients enrolled on this trial must be treated and followed at the participating centre. This implies there must be reasonable geographical limits (for example: 1 ½ hour's driving distance) placed on patients being considered for this trial. The patient's city of residence may be required to verify their geographical proximity. Call the CCTG office [contact]) if questions arise regarding the interpretation of this criterion. Investigators must assure themselves the patients enrolled on this trial will be available for complete documentation of the treatment, adverse events, and follow-up.

Patients must agree to return to their primary care facility for any adverse events and response assessment which may occur through the course of the trial.

- 4.1.13 In accordance with CCTG policy, protocol treatment is to begin within 2 working days of patient enrollment.
- 4.1.14 Women of childbearing potential must have agreed to use a highly effective contraceptive method. A woman is considered to be of "childbearing potential" if she has had menses at any time in the preceding 12 consecutive months. In addition to routine contraceptive methods, "effective contraception" also includes heterosexual celibacy and surgery intended to prevent pregnancy (or with a side-effect of pregnancy prevention) defined as a hysterectomy, bilateral oophorectomy or bilateral tubal ligation, or vasectomized partner. However, if at any point a previously celibate patient chooses to become heterosexually active during the time period for use of contraceptive measures outlined in the protocol, she is responsible for beginning contraceptive measures.

Female patients of childbearing potential who are sexually active with a non-sterilized male partner must use at least one highly effective method of contraception (failure rate of < 1% per year) while on study and for 3 months after the last dose of CFI-400945 and durvalumab. Cessation of birth control after this point should be discussed with a responsible physician. See Section 9.3 for additional details.

Women of childbearing potential will have a pregnancy test to determine eligibility as part of the Pre-Study Evaluation (see Section 5.0); this may include an ultrasound to rule-out pregnancy if a false-positive is suspected. For example, when beta-human chorionic gonadotropin is high and partner is vasectomized, it may be associated with tumour production of hCG, as seen with some cancers. Patient will be considered eligible if an ultrasound is negative for pregnancy.

- 4.1.15 Subjects should not donate blood while participating in this study, or for at least 90 days following the last infusion of durvalumab.

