- 1 Adverse events felt to be related to protocol therapy will be followed until resolved to \leq Grade 2. Reversible durvalumab- related adverse events \geq grade 3 should be followed until resolved to baseline grade including related toxicity that occurs in the follow up period. Irreversible events may not need to be followed. Contact CCTG to discuss. Adverse Events to be evaluated using the NCI Common Terminology Criteria for Adverse Events (CTCAE v5.0) (see Appendix V).
- 2 Height is only required at baseline.
- 3 Hematology is to be done twice weekly cycles 1 and 2. Provided patient has not experienced grade 3 or 4 neutropenia, hematology can be done weekly cycle 3 onward. For patients on for 6+ cycles, contact CCTG for a waiver if appropriate. See section 7 for additional monitoring of patients with toxicity.
- 4 Required at 4 weeks. To be done additionally every 3 months thereafter to follow abnormal lab results felt related until resolved to \leq Grade 2.
- 5 If creatinine $> 1.5 \times$ ULN, calculated CrCl is required and must meet eligibility criteria for re-treatment. For patients who have discontinued CFI-400945 and are continuing on durvalumab alone, criteria for creatinine clearance may be lower. Please contact CCTG to discuss.
- 6 Required at baseline then as clinically indicated. It is preferable that both amylase and lipase parameters are assessed. For sites where only 1 of these parameters is routinely measured then either lipase or amylase is acceptable.
- 7 Free T3 and free T4 will be measured if TSH is abnormal.
- 8 For women of childbearing potential only (urine or serum test). Within 72 hours prior to enrollment. Pregnancy test (in women of childbearing potential), as part of Pre-Study Evaluation, may include an ultrasound to rule-out pregnancy.
- 9 As clinically indicated in WOCBP.
- 10 Required at baseline then as clinically indicated.
- 11 Bone scan is required at baseline for all patients. Thereafter, bone scan is only required to be repeated if positive at baseline to confirm CR/iCR, PR/iPR or SD/iSD, and/or when PD is suspected and as clinically indicated.
- 12 To ensure comparability, baseline scans and subsequent scans to assess response must be performed using identical technique (i.e. scans performed immediately following bolus contrast administration using a standard volume of contrast, the identical contrast agent, and preferably the same scanner). Maintain schedule every 8 weeks, even if cycles are delayed.

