9.3 Other Protocol Reportable Events – Pregnancy Reporting and Exposure Reporting

9.3.1 Pregnancy Prevention

Women of Childbearing Potential (WOCBP) who are enrolled in the trial must have agreed to use contraceptive method(s) as described in Eligibility Criterion 4.1.14.

Females of childbearing potential are defined as those who are not surgically sterile (i.e. bilateral tubal ligation, bilateral oophorectomy, or complete hysterectomy) or post-menopausal (defined as 12 months with no menses without an alternative medical cause).

A highly effective method of contraception is defined as one that results in a low failure rate (i.e. less than 1% per year) when used consistently and correctly. Highly effective methods of contraception are described in the table below. Note that some contraception methods are not considered highly effective (e.g. male or female condom with or without spermicide; female cap, diaphragm, or sponge with or without spermicide; non-copper containing intrauterine device; progestogen-only oral hormonal contraceptive pills where inhibition of ovulation is not the primary mode of action (excluding Cerazette/desogestrel which is considered highly effective); and triphasic combined oral contraceptive pills).

Highly Effective* Methods of Contraception	
Barrier/Intrauterine Methods	Hormonal Methods

 • Copper T intrauterine device • Levonorgestrel-releasing intrauterine system (e.g. Mirena®)** 	
 • “Implants”: Etonogestrel-releasing implants: e.g. Implanon® or Norplan® • “Intravaginal Devices”: Ethinylestradiol/etonogestrel-releasing intravaginal devices: e.g. NuvaRing® • “Injection”: Medroxyprogesterone injection: e.g. Depo-Provera® • “Combined Pill”: Normal and low dose combined oral contraceptive pill • “Patch”: Norelgestromin/ethinylestradiol-releasing transdermal system: e.g. Ortho Evra® • “Minipill***”: Progesterone based oral contraceptive pill using desogestrel e.g. Cerazette®

* Highly effective (i.e. failure rate of <1% per year). ** This is also considered a hormonal method. *** Cerazette® is currently the only highly effective progesterone based pill.
	

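### Childbearing potential is defined one way in 4.1.14 and another in 9.3.1, and neither definition is stated to govern the pregnancy test or the contraception agreement

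*Combined protocol and SAP*

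**What the plan says.** Two places define the term.

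- **Criterion 4.1.14** (Section 4.1, Eligibility Criteria) considers a woman to be of childbearing potential "if she has had menses at any time in the preceding 12 consecutive months". Why menses may have stopped plays no part. The same criterion lists hysterectomy, bilateral oophorectomy and bilateral tubal ligation as forms of effective contraception.
- **Section 9.3.1** (Pregnancy Prevention) reads "Females of childbearing potential are defined as those who are not surgically sterile", with tubal ligation, oophorectomy and hysterectomy given as the sterilising procedures, or "post-menopausal (defined as 12 months with no menses without an alternative medical cause".

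Two requirements depend on the term.

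- **The pregnancy test.** 4.1.14 states: "Women of childbearing potential will have a pregnancy test to determine eligibility as part of the Pre-Study Evaluation". Footnote 8 to the Section 5 flowsheet repeats it: "For women of childbearing potential only (urine or serum test). Within 72 hours prior to enrollment". Footnote 9 makes on-study testing, when clinically indicated, depend on the same term. Neither footnote defines it.
- **Contraception.** 4.1.14 states: "Women of childbearing potential must have agreed to use a highly effective contraceptive method". Section 9.3.1 restates the obligation and refers to 4.1.14 for the methods.

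The two sections point to each other: 4.1.14 sends the reader to 9.3 for further detail, and 9.3.1 sends the reader back to 4.1.14. Neither says whose definition applies if they differ.

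**The concern.** A screening rule should give the same answer wherever a site looks it up. Here one patient can be in or out of the category depending on the section consulted. Section 6.1 requires sites to confirm the Section 4.0 requirements at enrollment, so 4.1.14 is the natural place to look, and 4.1.14 ignores the cause of amenorrhoea.

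The situation is foreseeable in this population. Only women enrol, from age 18, and 4.1.10 states: "Patients must have had at least 1 prior line of cytotoxic chemotherapy for breast cancer, in any setting". Absence of menses with a medical explanation is the circumstance that the qualifier in 9.3.1 addresses and that 4.1.14 passes over.

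What is at stake is participant safety and correct application of exclusion 4.2.7 (pregnancy). A site screening from 4.1.14 as written could leave untested, and without a contraception agreement, a woman whom 9.3.1 counts as of childbearing potential. Section 2.0 describes CFI-400945 as acting on mitotic progression and inducing aneuploidy, so fetal exposure would be a serious matter.

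**Working it through.** No sample size, error rate or event count enters this point, and the plan gives no figure to reproduce. The check treats the two definitions as logical rules and runs the same patients through both.

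**Rule A (4.1.14):** of childbearing potential = menses within the last 12 months.

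**Rule B (9.3.1):** of childbearing potential = not surgically sterile AND not (12 months without menses and no alternative medical cause).

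| Patient | Rule A | Rule B | Result |
|---|---|---|---|
| 1. Menses within 12 months, not sterilised | Yes | Yes | Agree |
| 2. More than 12 months without menses, no alternative medical cause | No | No | Agree |
| 3. More than 12 months without menses from a medical cause, not sterilised | No | Yes | **Conflict** |
| 4. Tubal ligation, menses within 12 months | Yes | No | **Conflict, opposite direction** |
| 5. Hysterectomy or bilateral oophorectomy more than 12 months ago | No | No | Agree |

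The consequences in the two conflicting rows are as follows.

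**Row 3.** Under Rule A neither the footnote 8 test nor the contraception agreement applies to her. If Rule B is carried into 4.1.14 and the Section 5 footnotes, both apply. Actual use of a highly effective method is narrower than the agreement: 4.1.14 requires it of women sexually active with a non-sterilised male partner, and it accepts heterosexual celibacy.

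**Row 4.** Under Rule A she is in the category, but 4.1.14 already accepts her ligation as contraception, so that requirement is met. Under Rule B she is outside the category altogether. The only practical difference is whether she has a pregnancy test.

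**Do the cross-references settle it?** A site that follows the pointer from 4.1.14 finds a second definition, with no statement that it replaces or supplements the first. A site that starts at 9.3.1 is sent back to 4.1.14 for methods and meets the first definition there. Footnotes 8 and 9 take neither side.

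**How many patients?** The documents give no age distribution and no frequency of amenorrhoea lasting more than 12 months after chemotherapy. The number still to be screened is also unclear. Section 3.1.4 reports 5 + 6 + 8 = 19 patients enrolled at earlier dose levels. If they count toward the stated maximum of 28, then 28 − 19 = 9 places remain, but the documents do not say whether they count. A count would rest on assumption at every step, so none is given.

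**The case against.** The best case on the other side is that the two texts can be read together. 4.1.14 says if, not only if, so strictly it names one sufficient condition. It also refers the reader to Section 9.3, where the fuller definition stands. A careful site could combine them and classify the row 3 patient as 9.3.1 does. In addition, pregnancy excludes a patient under 4.2.7 however she is classified, and 9.3.2 requires any pregnancy in a participant to be reported.

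Part of this stands. The sections are linked, and the route to an undetected exposure is narrower than the definitions alone suggest. But the sentence in 4.1.14 reads as a definition, the reference to 9.3 is for additional details and gives 9.3 no precedence, and the test is how 4.2.7 is checked at screening. A combined reading is possible, but nothing instructs a site to adopt it.

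The documents do not support some stronger readings that a reader might infer:

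- *That 9.3.1 itself requires the test.* It orders none. The test is ordered in 4.1.14 and Section 5, and reaches the row 3 patient only if the 9.3.1 definition is applied there.
- *That amenorrhoea from a hormonal intrauterine system shows the same gap in contraception.* 9.3.1 lists the levonorgestrel-releasing system as highly effective, so that woman already uses an accepted method and only her test is in question.
- *That tubal ligation exposes an equal and opposite risk.* As row 4 shows, only the test differs.
- *That long amenorrhoea is typical here, or that a particular number of the 28 patients is affected.* 4.1.10 establishes prior chemotherapy. It does not establish how often prolonged amenorrhoea follows.

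**Conclusion.** The contradiction is real and in the current text. The two definitions disagree for non-sterilised women with more than 12 months of amenorrhoea from a medical cause and, with little consequence, for menstruating women with a tubal ligation. Neither definition is stated to govern, although an eligibility test and a contraception obligation depend on the answer.

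The conclusion rests on the wording of 4.1.14, 9.3.1 and the Section 5 footnotes, and on no assumed frequency. Its size in patients cannot be estimated from the documents. It concerns participant safety and consistent application of eligibility. The two-stage response-rate design (15, then 28 patients) and its decision rules are untouched. It is a limited inconsistency, worth correcting because it bears on safety and is cheap to correct. Which definition is clinically right is for the sponsor to decide.

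**What to change.** Reconcile 4.1.14 and 9.3.1 to one definition of childbearing potential, stated once.

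1. State the chosen definition in one of the two sections, and replace the wording in the other with a cross-reference that makes clear it governs.
2. Have footnotes 8 and 9 of the Section 5 flowsheet refer to the same place.
3. Say explicitly how the definition classifies amenorrhoea with a medical cause and how it classifies tubal ligation, since these are the cases on which the present texts divide.

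The cost is one sentence and a cross-reference. Depending on the definition chosen, there may be a few extra urine or serum pregnancy tests. No change to the sample size, endpoints or analysis is needed.

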4.2 Ineligibility Criteria

Patients who fulfill any of the following criteria are not eligible for admission to the study:

- 4.2.1 Patients with a history of other malignancies, except: adequately treated non-melanoma skin cancer, curatively treated in-situ cancer of the cervix, or other solid tumours curatively treated with no evidence of disease for > 2 years and which do not require ongoing treatment.
- 4.2.2 Patients with serious illnesses or medical conditions which would not permit the patient to be managed according to the protocol (including corticosteroid administration), or would put the patient at risk. This includes but is not limited to:
- History of significant neurologic or psychiatric disorder which would impair the ability to obtain consent or limit compliance with study requirements.
 - Active infection requiring systemic therapy; (including any patient known to have active hepatitis B, hepatitis C or human immunodeficiency virus (HIV) or tuberculosis or any infection requiring systemic therapy).
 - Active peptic ulcer disease or gastritis.
 - Known pneumonitis or pulmonary fibrosis with clinically significant impairment of pulmonary function.
 - Patients with diabetes mellitus are eligible but must be clinically stable on therapy (if applicable) and investigator and patient should be aware of the potential risk of immune mediated pancreatic toxicity and B cell destruction.
- 4.2.3 Patients are not eligible if they have a known hypersensitivity to the study drug(s) or their components.
- 4.2.4 Patients who have experienced untreated and/or uncontrolled cardiovascular conditions and/or have symptomatic cardiac dysfunction (unstable angina, congestive heart failure, myocardial infarction within the previous year or cardiac ventricular arrhythmias requiring medication, history of 2nd or 3rd degree atrioventricular conduction defects). Patients with a significant cardiac history, even if controlled, should have a LVEF \geq 50%.
- 4.2.5 Patients may not receive concurrent treatment with other anti-cancer therapy (other than bone-targeted therapy, if already taking and stable) or investigational agents while on protocol therapy.
- 4.2.6 Patients who have received growth factors within 28 days prior to initiation of dosing of CFI-400945 or who will require treatment with growth factors throughout the duration of the trial.
- 4.2.7 Pregnant or breastfeeding women.
- 4.2.8 Patients being treated with drugs listed in Appendix VI Table 1 are excluded. Patients being treated with drugs listed in Appendix VI Table 2 may be enrolled, but should be monitored carefully for toxicities resulting from potential interactions between CFI-400945 and these drugs. In addition, patients must avoid consumption of the fruit or juice of Seville oranges (e.g. marmalade), grapefruit, pomelos and star fruit from 7 days before the first dose of study drug and during the entire study due to potential CYP3A4 interaction with the study drug. Regular orange juice is allowed.

- 4.2.9 Patients with history of central nervous system metastases or spinal cord compression unless they have received definitive treatment, are clinically stable and do not require corticosteroids.
- 4.2.10 Patients with any medical condition that would impair the administration of oral agents including significant bowel resection, inflammatory bowel disease or uncontrolled nausea or vomiting.
- 4.2.11 Active or prior documented autoimmune or inflammatory disorders including inflammatory bowel disease (e.g. colitis or Crohn's disease), diverticulitis with the exception of diverticulosis, celiac disease or other serious gastrointestinal chronic conditions associated with diarrhea), systemic lupus erythematosus, Sarcoidosis syndrome, or Wegener syndrome (granulomatosis with polyangiitis), rheumatoid arthritis, hypophysitis, uveitis, etc., within the past 3 years prior to the start of treatment. The following are exceptions to this criterion:
- Patients with alopecia.
 - Patients with Grave's disease, vitiligo or psoriasis not requiring systemic treatment (within the last 2 years).
 - Patients with hypothyroidism (e.g. following Hashimoto syndrome) stable on hormone replacement.
- 4.2.12 History of primary immunodeficiency, history of allogenic organ transplant that requires therapeutic immunosuppression and the use of immunosuppressive agents within 28 days of enrollment *.
- * *NOTE: Intranasal/inhaled corticosteroids or systemic steroids that do not to exceed 10 mg/day of prednisone or equivalent dose of an alternative corticosteroid are permissible.*
- 4.2.13 Live attenuated vaccination administered within 30 days prior to enrollment or within 30 days of receiving durvalumab.
- 4.2.14 Any previous treatment with a PD-1 or PD-L1 inhibitor, including durvalumab or an anti-CTLA4.
- 4.2.15 Patients being treated with full dose warfarin. Patients with history of deep vein thrombosis or pulmonary embolus who are being treated with therapeutic doses of low molecular weight heparin, direct factor Xa inhibitors or prophylactic dose anticoagulants may be enrolled.

5.0 PATIENT EVALUATION FLOWSHEET: PRE-TREATMENT, ON STUDY, AND AFTER TREATMENT

All patients entered on study must be evaluated according to the schedule outlined below with documentation submitted according to the schedule in Appendix IV.

Required Investigations	Pre-study (≤ 7 days prior to enrollment)	Biweekly cycles 1 and 2 and then Weekly	Day 1 each cycle, and as clinically indicated	Every 8 weeks	4 weeks after end of last cycle date	3 monthly follow-up (only required for pts without PD and ongoing toxicities ¹) then every 6 months until death
History and Physical Exam*						
Including: height ² and weight, ECOG performance status, documentation of all measurable and non-measurable disease, clinical tumour measurements (if applicable); Vital signs: blood pressure, heart rate, temperature	X		X		X	
Laboratory Procedures/Assessments*						
CBC (neutrophils, platelets)	X	X ³			X ⁴	X ⁴
PTT, PT/INR	X					
Serum creatinine ⁵ , calcium, magnesium, phosphate, bilirubin, ALP, AST, ALT, LDH, albumin, glucose, amylase/lipase ⁶	X		X		X ⁴	X ⁴
TSH ⁷	X		X		X ⁴	X ⁴
Pregnancy Test ⁸	X		X ⁹			
Urinalysis	X ¹⁰					
Radiology						
Tumour Imaging (Chest/upper abdomen CT scan; bone scan ¹¹ ; other scans as necessary to document disease) ¹²	X ¹³ (within 21 days prior to enrollment or 28 days if negative)			X	X ¹⁴	X ¹⁴
Other Investigations						
EKG	X					
LVEF	X ¹⁰					
Archival Tumour Tissue	X ¹⁵					
Correlative Studies Blood Sampling	X ¹⁶	See Section 12.0 for details				
Tumour biopsies	X ¹⁷	X ¹⁷				
Patient Drug Administration Diary (CFI-400945)		Each cycle				
Adverse events	X	Continuously			X ¹	

Footnotes on next page ...

- * Pre-treatment blood draws and physical exams may be done up to two working days prior to treatment if necessary (e.g. Friday for treatment on Monday, or to accommodate holidays). In order to ensure that nadir counts are not missed, every effort should be made to do interim blood draws within 24 hours of the day specified in the protocol. If a patient shows an AST or ALT $\geq 3 \times$ ULN together with total bilirubin $\geq 2 \times$ ULN, refer to Appendix II for further instructions on cases of increases in liver biochemistry and evaluation of Hy's Law. These cases should be reported as SAEs if, after evaluation, they meet the criteria for a Hy's law case or if any of the individual liver test parameters fulfill any of the SAE criteria
- 1 Adverse events felt to be related to protocol therapy will be followed until resolved to \leq Grade 2. Reversible durvalumab- related adverse events \geq grade 3 should be followed until resolved to baseline grade including related toxicity that occurs in the follow up period. Irreversible events may not need to be followed. Contact CCTG to discuss. Adverse Events to be evaluated using the NCI Common Terminology Criteria for Adverse Events (CTCAE v5.0) (see Appendix V).
- 2 Height is only required at baseline.
- 3 Hematology is to be done twice weekly cycles 1 and 2. Provided patient has not experienced grade 3 or 4 neutropenia, hematology can be done weekly cycle 3 onward. For patients on for 6+ cycles, contact CCTG for a waiver if appropriate. See section 7 for additional monitoring of patients with toxicity.
- 4 Required at 4 weeks. To be done additionally every 3 months thereafter to follow abnormal lab results felt related until resolved to \leq Grade 2.
- 5 If creatinine $> 1.5 \times$ ULN, calculated CrCl is required and must meet eligibility criteria for re-treatment. For patients who have discontinued CFI-400945 and are continuing on durvalumab alone, criteria for creatinine clearance may be lower. Please contact CCTG to discuss.
- 6 Required at baseline then as clinically indicated. It is preferable that both amylase and lipase parameters are assessed. For sites where only 1 of these parameters is routinely measured then either lipase or amylase is acceptable.
- 7 Free T3 and free T4 will be measured if TSH is abnormal.
- 8 For women of childbearing potential only (urine or serum test). Within 72 hours prior to enrollment. Pregnancy test (in women of childbearing potential), as part of Pre-Study Evaluation, may include an ultrasound to rule-out pregnancy.
- 9 As clinically indicated in WOCBP.
- 10 Required at baseline then as clinically indicated.
- 11 Bone scan is required at baseline for all patients. Thereafter, bone scan is only required to be repeated if positive at baseline to confirm CR/iCR, PR/iPR or SD/iSD, and/or when PD is suspected and as clinically indicated.
- 12 To ensure comparability, baseline scans and subsequent scans to assess response must be performed using identical technique (i.e. scans performed immediately following bolus contrast administration using a standard volume of contrast, the identical contrast agent, and preferably the same scanner). Maintain schedule every 8 weeks, even if cycles are delayed.
- 13 In order to evaluate tumour growth rate, if additional imaging was done prior to baseline radiology (done 3-12 weeks prior to Baseline scan), scans should also be evaluated according to RECIST 1.1 criteria and submitted with baseline reports. Note selection of target and/or non-target lesions is based on baseline imaging only. The same lesions (target and/or non-target) selected on baseline imaging should then be assessed on the pre-baseline scans if present.
- 14 To be done every three months until relapse or progression (iCPD), for patients with CR/iCR, PR/iPR, SD/iSD response as defined in Section 8.0. Patients with CR/iCR or PR/iPR or equivocal PD (pseudoprogression)/iUPD should have scans repeated after 4 weeks, but no more than 8 weeks, to confirm response.
- 15 Must be confirmed available prior to enrollment on ALL patients. See Section 12.0 for details.
- 16 After enrollment but before the first dose of study treatment. Please refer to Section 12 and the Correlative Studies Manual for details regarding collection.
- 17 Optional paired biopsies should be obtained after enrollment (unless biopsy with available block within 90 days of enrollment) but prior to first dose and Cycle 3 (D1-8). Biopsies are also strongly recommended in all consenting patients when radiological disease progression on therapy is confirmed among patients who had initial response of CR/iCR, PR/iPR or SD/iSD greater than 4 months. See Section 12.1 for details.

